## 7. DATA ANALYSIS/STATISTICAL METHODS

The details of the data analysis will be documented in a Statistical Analysis Plan (SAP) document, which will be maintained by the sponsor. The SAP will elaborate, and may modify the analytic plans outlined in the protocol; however, any major modifications will be reflected in a protocol amendment.

### 7.1. Sample Size Calculation

There is no active de novo patient enrollment in this study and all women in the database who meet the inclusion criteria during the recruitment period will be included in the analysis. Therefore, the focus of the sample size calculation was to determine the precision of the estimated incidence rate ratios (IRR) that can potentially be achieved in the study depending on several different hypothetical scenarios of subject accrual. Depending on drug uptake in the participating countries, speed of accrual, event rates, and actual dropout rates, the precision of the estimated incidence rate ratio may change.

The estimates are based on the expected incidence rate of VTE as the primary endpoint. It is estimated that the incidence rate of VTE in women who are not treated with a SERM or HT is 1.74/1000 patient-years (PY), based on data from the placebo groups in bazedoxifene clinical trials. It is assumed that women treated with raloxifene would have a higher incidence of VTE, of 2.17/1000 PY, based on data from the Phase III pivotal trials of bazedoxifene. The rate of VTE observed in the raloxifene arm of the bazedoxifene pivotal trials is lower than the rate reported in the Multiple Outcomes of Raloxifene Evaluation (MORE) trial [1]. In the MORE trial, the incidence rate of VTE was 3.5/1000 patient-years in women randomized to raloxifene. Therefore, our calculations are likely to be substantially more conservative than estimates based on rates in the literature.

All estimates (Table 3, Table 4) were calculated with two-sided 95% confidence intervals. According to the study plan, there will be a 3-year accrual period and each woman will be followed for up to 5 years from enrollment. Since osteoporosis therapies are chronic therapies, it is likely that women will be exposed to the drugs for more than one year. A conservative annual loss to follow up rate of 15% was used in the estimation. Estimates were based on Wald 95% confidence intervals [2]

**Table 3: 95% Confidence Intervals (CI) for Incidence Rate Ratios (IRR) with different numbers of patients in the BZA arm and the primary comparator arm**

Bazedoxifene (n)	Bisphosphonate (n)	BZA:Bisphosphonate	Underlying Incidence Rate Ratio (IRR)		
			1	1.5	2
			95% CI of observed point estimate of IRR		
2150	8600	1:4	0.6, 1.7	1.0, 2.4	1.3, 3.0
2000	8000	1:4	0.6, 1.8	0.9, 2.4	1.3, 3.1
1750	10,500	1:6	0.6, 1.8	0.9, 2.5	1.3, 3.1
1500	12,000	1:8	0.5, 1.9	0.9, 2.5	1.3, 3.2

The estimated 95% CI of the incidence rate ratios (IRR) in Table 3 imply that if the underlying (true) IRR comparing BZA users to bisphosphonate users is 2, then the point estimate of IRR in the study will lie between 1.3 and 3.2 indicating (a) that the study will be able to rule out equality of the IRRs (i.e., IRR>1) and (b) that the study would not be able to rule out the possibility that the true IRR could be as high as 3.2 or as low as 1.3.

**Table 4: 95% Confidence Intervals (CI) for Incidence Rate Ratios (IRR) comparing BZA users and Raloxifene users assuming equal number of patients in the two arms**

Bazedoxifene (n)	Raloxifene (n)	BZA:Raloxifene	Incidence Rate Ratio (IRR)		
			1	1.5	2
			95% CI of observed point estimate of IRR		
2150	2150	1:1	0.5, 1.9	0.9, 2.7	1.2, 3.4

The estimated 95% CI of the incidence rate ratio (IRR) in table 4 implies that if the underlying (true) IRR comparing BZA users to raloxifene users is 2, then the point estimate of IRR in the study will lie between 1.2 and 3.4 indicating (a) that the study will be able to rule out equality of the IRRs (i.e., IRR>1) and (b) that the study would not be able to rule out the possibility that the true IRR could be as high as 3.4 or as low as 1.2.

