## **2.2. Endpoints**

The clinical endpoints for this study were determined based on the clinical and pre-clinical data from the bazedoxifene development program, class effects of other SERMs, and recommendations of the EU Rapporteurs.

Potential endpoints will be identified by an electronic search of the coded diagnosis fields of the medical records. The relevant diagnostic codes that will be used as operational definitions of each of the endpoints will be listed in the statistical analytic plan of the study. The available medical record of the identified cases for the primary endpoint will be retrieved and reviewed to confirm the diagnosis.

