**Table 2: Data coding conventions in the different countries**

	France	UK	Italy	Germany	Spain
Drug code dictionary	Claude Bernard	Multilex	Farmadati	Abdata	Vademecum
Therapy classification	European Pharmaceutical Marketing Research Association (EphMRA)	British National Formulary (BNF)	Anatomical Therapeutic Chemical (ATC)	ATC	ATC
Disease classification	Home grown thesaurus mapped to International Classification of Diseases-10 (ICD-10) and International Classification of Primary Care-2 (ICPC-2)	Read Codes	ICD-9	ICD-10	Code CIAP mapped to ICD-9

Cegedim LPD does not collect hospitalization data directly except in the UK THIN database. Information on hospitalizations is captured in the patient's general practice file during follow-up visits with the patient's general practice physician following discharge from the hospital. However, this information is not systematically collected and there is no established linkage between the medical records at the general practices and at the hospitals.

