## 10. POTENTIAL WEAKNESSES

**Lack of hospitalization data:** The Cegedim LPD collects data from GP offices. Therefore, complete records of events requiring hospitalization are not available in the database. Since no patient identifiers are available it is also not possible to link to any available national or regional registries to obtain additional information (e.g., vital status, diagnosis of malignancies).

**Data collection in routine care:** The Cegedim LPD collects real life clinical practice information from the actual medical records of the patients. No study specific CRF will be used to collect supplemental information that are not entered in the medical records as part of the patient's routine clinical care. Also, as a non-interventional study, this protocol does not mandate any study specific visits, procedures or laboratory tests.

**Dependence on market uptake of the study medication:** Bazedoxifene is a newly launched product in the participating countries. Since there is no active enrollment of patients (i.e., in contrast to a de novo prospective follow up study), the final sample size will be based on the rate of the uptake of the drug in the participating countries during the subject accrual period.

**Potential for missing data:** The data for this study will come from routine clinical care. No individual patient identifiers will be available. Therefore it is not possible to query the physicians providing the data for any missing information.

**Difference in indication for Bazedoxifene and Raloxifene:** Bazedoxifene is indicated for the treatment of post-menopausal osteoporosis whereas Raloxifene is indicated for both the prevention and treatment of post-menopausal osteoporosis. As a result the characteristics of the cohort of women receiving Raloxifene may differ from the women who are receiving Bazedoxifene. It is possible that the Raloxifene cohort will have a higher proportion of healthier, younger women.

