5.4 SUBGROUPS

Age stratified randomly selected subgroup

In the current dataset, there are 1,823 patients in the bazedoxifene group and 82,041 patients in the bisphosphonate group. This means that there is more than 40 times the number of subjects in the bisphosphonate group compared to the number of subjects in the bazedoxifene group. To limit the number of patients in the bisphosphonate group, an age stratified random subgroup will be selected. Based on the sample size and relative risk estimates provided in the final study protocol (study protocol section 7.1, Sample size calculation), the 1,823 bazedoxifene subjects will be adequately matched by a ratio of 1:6 bisphosphonate subjects. Therefore $1,823 \times 6 = 10,938$ bisphosphonate treated subjects are needed to be randomly selected from the total of 82,041 bisphosphonate treated subjects.

Selection scheme: The age of subjects in the study will be categorized into 4 groups (45-49, 50-59, 60-69, and ≥ 70). In the bisphosphonate group, the percentage of subjects in each of these age groups is 1.4%, 13.7%, 28.7%, and 56.2% respectively. To maintain the same proportion of subjects in each age group for the bisphosphonate subgroup, there will be $1.4\% \times 10,938 = 153$ bisphosphonate treated subjects randomly selected from the 45-49 age group; $13.7\% \times 10,938 = 1,499$ subjects randomly selected from the 50-59 age group; $28.7\% \times 10,938 = 3,139$ subjects randomly selected from the 60-69 age group; $56.2\% \times 10,938 = 6,147$ subjects randomly selected from ≥ 70 age group.

Incident cases of study endpoints

Women with a history of study end points recorded prior to the index prescription will not be included in the analysis for that specific outcome, but will be analyzed separately as subgroups for each study end point. The analyses of the primary and secondary endpoints will be performed using these incident cases of study endpoints subgroups.

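### Protocol 7.1 calls its precision tables conservative and says equality will be ruled out, with no allowance for VTEs that the GP record misses and on a rate that does not enter the primary comparison

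*Protocol*

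**What the plan says.** Protocol 7.1 sets the comparator rate for Table 3 at 1.74 per 1000 patient-years, "based on data from the placebo groups in bazedoxifene clinical trials". The raloxifene rate for Table 4 is 2.17, from the Phase III bazedoxifene trials. The only stated reduction is a 15% annual loss to follow-up. The section notes that a published raloxifene trial found 3.5 and concludes that "our calculations are likely to be substantially more conservative than estimates based on rates in the literature". From the tables it infers, for a true ratio of 2 and for each comparator, that "the study will be able to rule out equality of the IRRs".

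Other parts of the protocol describe how a VTE comes to be counted:

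- Section 3.2, on hospital information in the GP file: "this information is not systematically collected and there is no established linkage between the medical records at the general practices and at the hospitals".
- Section 10: "complete records of events requiring hospitalization are not available in the database". It adds that physicians cannot be asked about missing information.
- Section 2.2: the available records of VTE cases found by code "will be retrieved and reviewed to confirm the diagnosis".

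SAP 2.1 adds that the Spanish and Italian data do not record death. SAP 3 takes the precision in protocol 7.1 as the level to preserve. SAP 5.4 cites the same section when it sets the comparator sample: "the 1,823 bazedoxifene subjects will be adequately matched by a ratio of 1:6 bisphosphonate subjects".

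**The concern.** Precision here depends on the number of counted events, which is the true rate times the share recorded and confirmed. Section 7.1 uses a trial rate for the first factor and, without saying so, 100% for the second. The protocol's own account of the database makes 100% implausible for a diagnosis that may be made in hospital.

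The claim of conservatism does not fill the gap. It compares one trial's raloxifene rate with another's, so it says nothing about capture in GP files. It also concerns raloxifene only. Table 3 uses 1.74, and no literature rate is offered against it.

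At stake is how a null or raised ratio will be read. A regulator who takes the tables at face value may believe that a doubling of VTE would be detected, or excluded, more reliably than the data allow.

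**Working it through.** **Inputs from the documents.** Rates of 1.74, 2.17 and 3.5 per 1000 patient-years (PY), two-sided 95% Wald intervals, follow-up of up to 5 years and 15% annual loss (protocol 7.1). Group sizes 2,150:2,150 (Table 4) and 1,823:10,938 (SAP 5.4).

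**Assumption.** Let c be the share of true VTEs both recorded and confirmed. The documents give no value, so a range is shown. It is taken as equal in the two groups, with no false positives.

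**Formulas.**
- Events: E0 = n0 × PY × rate × c / 1000 and E1 = n1 × PY × rate × IRR × c / 1000.
- SE of log IRR = √(1/E1 + 1/E0). Limits = IRR × exp(±1.96 SE).
- Probability of excluding 1 = Φ(ln IRR / SE − 1.96).
- The expected lower limit equals 1 at c = SE² (at c = 1) ÷ (ln 2 / 1.96)², where (ln 2 / 1.96)² = 0.125.

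**Reproducing the plan.** With c = 1, 4.35 PY per woman gives 23 of the 24 limits in Table 3 to one decimal. A single 15% reduction, 5 × 0.85 = 4.25 PY, gives 22 of 24. At either value every limit in Tables 3 and 4 agrees within about 0.07. So the tables use the full trial rates, and no capture discount is hidden in them. Read literally, 15% loss each year over 5 years gives (1 − 0.85⁵)/(−ln 0.85) = 3.42 PY, which does not reproduce the tables. It is carried below as a second case.

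**Worked example, 1,823:10,938, IRR 2, c = 1, 4.35 PY.**
- E1 = 1,823 × 4.35 × 1.74 × 2 / 1000 = 27.6.
- E0 = 10,938 × 4.35 × 1.74 / 1000 = 82.8.
- SE = √(1/27.6 + 1/82.8) = 0.220.
- Limits 1.30 and 3.08. Probability Φ(0.693/0.220 − 1.96) = 88%.
- Break-even c = 0.0483/0.125 = 39%.

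**Results at IRR 2 and 4.35 PY: 95% range (probability of excluding 1).**

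| Comparison | c = 100% | c = 75% | c = 50% | Lower limit reaches 1 at c = (at 3.42 PY) |
|---|---|---|---|---|
| 1,823:10,938, rate 1.74 | 1.30–3.08 (88%) | 1.22–3.29 (78%) | 1.09–3.68 (61%) | 39% (49%) |
| Table 4, rate 2.17 | 1.17–3.41 (72%) | 1.08–3.70 (60%) | 0.94–4.25 (44%) | 59% (75%) |
| Table 4, rate 3.5 | 1.31–3.04 (90%) | 1.23–3.25 (80%) | 1.10–3.62 (63%) | 37% (47%) |

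**At IRR 1**, 1,823:10,938 and 4.35 PY, the upper limit is 1.77 at c = 100% and 2.24 at c = 50%. In the second case a null result would no longer exclude a doubling.

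**The case against.** The strongest reply is that the net direction is unknown. SAP 5.4 puts 56.2% of bisphosphonate users at age 70 or over. The true VTE rate in routine care may exceed the trial rate and offset incomplete recording. This stands. A reader might infer that the tables certainly overstate precision; the documents do not show that the counted rate falls below 1.74. The same uncertainty leaves the claim of conservatism unsupported.

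Second, the primary comparison is fairly robust. At IRR 2 the expected interval for 1,823:10,938 still excludes 1 until about 61% of VTEs are lost, or 51% at 3.42 PY. This also stands. For Table 4, the margin the plan cites is real: 2.17/3.5 = 0.62, so at a true raloxifene rate of 3.5 the printed precision survives the loss of 38% of events.

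Third, the plan has safeguards. Section 7.1 calls its scenarios hypothetical and says precision may change with event rates, and section 10 discloses the missing hospital data. The interim analysis (protocol 7.3, SAP 3) uses observed VTE rates to decide whether to extend the study. These limit the harm. They do not correct a stated favourable direction, and the caveat names neither recording nor confirmation.

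Fourth, one might read SAP 5.4 as declaring 1,823 women enough. It does not. It calls the 1:6 ratio adequate, and a common c scales both event counts, so the efficiency of 1:6 relative to using every comparator does not depend on c.

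Finally, record review also removes false positives, which is no loss of true events. The documents do not say what share of true VTEs would fail it.

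**Conclusion.** The point holds in a limited form. Section 7.1 uses undiscounted trial rates although the protocol describes incomplete recording and a confirmation step. Its claim of conservatism has no basis for Table 3, and its statement that equality will be ruled out should be conditional. The first two need no assumed capture share. Nor does the third: even at c = 100% and 4.35 PY, the probability of excluding 1 at IRR 2 is 88% for the SAP's groups and 72% for Table 4.

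The sizes for c below 100% are illustrations. They rest on an assumed c that is equal between groups, on no false positives and on 4.35 PY per woman. On those assumptions the weaker comparison is raloxifene at 2.17, where the expected interval includes 1 once c falls below 59%.

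A reader might go further and infer that the study cannot detect a doubling against bisphosphonates, or that under-recording biases the ratio. Neither follows. Equal under-recording without false positives costs precision and leaves the ratio unbiased. This is an untested input, not an arithmetical error in the tables. It should be corrected but does not undermine the design.

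**What to change.** 1. In protocol 7.1, confine the sentence on conservatism to the raloxifene rate in Table 4.
2. Show Tables 3 and 4 over a range of counted VTE rates, for example 50%, 75% and 100% of the trial rate, with Table 4 also at 3.5. Say that the counted rate combines the true rate with recording and confirmation, and that neither is known in advance.
3. Replace the statement that equality will be ruled out with the probability of excluding 1 at each rate.
4. When the interim or final report states achieved precision, base it on the observed confirmed VTE rate. The interim check on observed rates can stay as planned.

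The cost is revised wording and a recalculated table, with no new data collection. The drawback for the sponsor is that the stated precision becomes less favourable.

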### **6. STUDY PROCEDURES**

#### **6.1. Follow up time and drug exposure time**

##### **6.1.1. Follow up:**

Each woman will be followed for identification of the selected endpoints for a period of up to five years from the date of the index prescription record for bazedoxifene, raloxifene or a bisphosphonate. The follow up will continue even if the woman discontinues the index medication or switches to a different medication during the five year period.

The follow up duration of an individual woman may be shorter than the five year period if the woman transfers out of her GP office that wrote the index prescription, or if the database records the death of the woman. In these situations the data will be censored on the date of transfer or the date of death.

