In this study the proportion and demographic and clinical characteristics of patients that switch medications between the study drugs will be reported alongside patients that do not switch medications. Both the AT and CR analytic approaches will be used for all study endpoints and the results reported. In the CR method, if a patient switches from one exposure (study drug) cohort group to another, they will have several treatment durations and will belong to multiple cohort groups but will be analyzed according to their original exposure cohort group (i.e., CR/intent to treat approach). In the AT approach, all exposure cohort groups will be included as a time-dependent variable. With the exposure cohort group as a time-dependent variable, each event will be assigned to the treatment being taken at the time of occurrence. The duration of treatment for each cohort group will be from the date of the first prescription to the date of the event or to the end of treatment, whichever occurs first. The covariates of patients that switched treatment at the time of the event or at the end of follow-up would be considered in this model.

[figure not shown]
The following diagrams shows some example of calculating duration for patients with switched treatments with both the AT and CR approaches.

Figure 2a. Calculating the duration of treatment for patients that switched treatment using the as-treated (AT) approach.

A, B, C: Treatment cohort types. X= Incidence date of primary end point

Figure 2b. Calculating the duration of treatment for patients that switched treatments using the cumulative risk (CR) approach.

A, B, C: Treatment cohort types. X= Incidence date of primary end point

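### Protocol Table 3 counts all follow-up as exposed and does not say which rate ratio it means, so its precision does not carry over to the as-treated analysis

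*Protocol*

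**What the plan says.** Protocol 7.1 takes a comparator VTE rate that "is 1.74/1000 patient-years (PY), based on data from the placebo groups in bazedoxifene clinical trials", follow-up of up to five years and 15% annual loss. "Estimates were based on Wald 95% confidence intervals". On exposure it offers only that "Since osteoporosis therapies are chronic therapies, it is likely that women will be exposed to the drugs for more than one year"; no persistence, stopping or switching figure enters. For a true ratio of 2 it reads Table 3 as "indicating (a) that the study will be able to rule out equality of the IRRs", without conditions.

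On what counts as follow-up, Protocol 6.1.1 says "The follow up will continue even if the woman discontinues the index medication or switches to a different medication during the five year period". Protocol 6.1.2 expects intermittent use, with current, recent and past time on several drugs.

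SAP 8.1.4 reports two analyses for every endpoint. The as-treated (AT) analysis counts each drug's time "to the date of the event or to the end of treatment, whichever occurs first". The cumulative-risk (CR) analysis keeps each woman on her first drug for all follow-up. The SAP notes that CR misclassification usually pulls the ratio towards the null, more so with longer follow-up and earlier stopping. SAP 8.1.2 uses ever-exposed person-time for the incidence-density rates.

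Two SAP sections lean on protocol 7.1. Section 3 makes its precision the benchmark for extending the study after the interim analysis. Section 5.4 cites it to call a 1:6 sample adequate (1,823 bazedoxifene, 10,938 bisphosphonate).

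**The concern.** A rate ratio and its confidence limits mean something only together with the person-time they refer to. Table 3 uses all follow-up, names no ratio as on-treatment or ever-exposed, and then promises that equality will be excluded. The AT analysis has less person-time, and so fewer events, as soon as women stop. The CR analysis has the person-time of Table 3, but its ratio is smaller than the on-drug ratio if risk returns to background after stopping.

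VTE is an identified risk of bazedoxifene, and this study is a regulatory commitment. If Table 3 is taken as the precision of whichever analysis is reported, a non-significant VTE result could reassure more than it should, and the interim and sampling decisions would be judged against a standard that the AT analysis may not meet.

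**Working it through.** **Inputs.** From protocol 7.1: comparator rate R = 0.00174 per person-year; two-sided 95% Wald limits, taken here on the log scale; true ratio 2. From SAP 5.4: 1,823 and 10,938 women. Mean on-drug time d is not given beyond exceeding one year, so 1, 1.5, 2 and 3 years are assumed, equal in both groups.

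**Formulas.** Expected events: a = n1 × PY × R × IRR (bazedoxifene) and b = n0 × PY × R (bisphosphonate). SE = √(1/a + 1/b). Limits = IRR × exp(±1.96 SE). Power = Φ(ln IRR / SE − 1.96), plus the negligible other tail.

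**Step 1: reproduce Table 3.** Scanning PY, the best agreement is at 4.33 to 4.36: 23 of 24 printed limits fall within 0.05. The exception is the lower limit at 2150:8600 and ratio 1.5, printed 1.0 against 0.94. At 4.25 PY, 22 of 24 agree. Example at 4.35 PY, 1750:10,500, ratio 2: 1.29 to 3.10, printed 1.3 to 3.1.

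Five years with 15% annual loss gives (1 − 0.85^5)/(−ln 0.85) = 3.42 PY, which matches few of the printed limits. That mismatch is a separate matter. Here it shows that Table 3 contains no off-drug deduction, and it is why results below are given for both 4.35 and 3.42 PY.

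**Step 2: every woman on drug throughout, ratio 2, SAP sample.**
- 4.35 PY: 27.6 and 82.8 events, limits 1.30 to 3.08, power 88%.
- 3.42 PY: 21.7 and 65.1 events, limits 1.23 to 3.25, power 80%.

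**Step 3: AT.** Set PY = d and keep the ratio at 2. For d = 1: a = 1,823 × 0.00174 × 2 = 6.3, b = 10,938 × 0.00174 = 19.0, SE = 0.458.

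**Step 4: CR, if 2 is the on-drug ratio.** With follow-up F and no excess risk off drug, bazedoxifene events per woman are R(2d + F − d) = R(F + d), so the CR ratio is 1 + d/F. For d = 2, F = 4.35: 1 + 2/4.35 = 1.46.

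| d (years) | AT events | AT limits | AT power | CR at 4.35 PY: ratio, limits, power | CR at 3.42 PY: ratio, limits, power |
|---|---|---|---|---|---|
| 1 | 6.3 / 19.0 | 0.81–4.91 | 33% | 1.23, 0.73–2.07, 12% | 1.29, 0.73–2.30, 14% |
| 1.5 | 9.5 / 28.5 | 0.96–4.17 | 46% | 1.34, 0.81–2.22, 21% | 1.44, 0.83–2.50, 25% |
| 2 | 12.7 / 38.1 | 1.06–3.78 | 57% | 1.46, 0.90–2.38, 33% | 1.58, 0.93–2.70, 40% |
| 3 | 19.0 / 57.1 | 1.19–3.36 | about 75% (74.5%) | 1.69, 1.07–2.68, 61% | 1.88, 1.14–3.09, 70% |

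**Step 5: break-even.** The expected AT lower limit passes 1 at about 1.7 on-drug years. Power there is about 50%, as it must be when the expected limit sits at the null.

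**Step 6: the other reading.** If 2 is the ever-exposed ratio, Table 3 needs no dilution for CR. The on-drug ratio behind it, under the same no-carry-over model, is then 1 + F/d; at d = 2, F = 4.35 that is 1 + 4.35/2 = 3.2.

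**The case against.** The strongest reply is that Table 3 already matches one reported analysis. Its person-time is that of protocol 6.1.1, of the ever-exposed rates in SAP 8.1.2 and of CR. Its column is headed as an underlying ratio, and the text compares users of the two drugs without saying on-drug. A reader might infer that Table 3 fits neither SAP analysis. The documents do not support that: with an ever-exposed ratio of 2, its person-time is the CR person-time and no dilution arises. What stands is that the protocol never says so, and that AT is not covered on either reading.

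Second, whether equality can be excluded depends on persistence, which the documents do not give. In the table, the expected lower limit still exceeds 1 for AT at 2 and 3 years and for CR at 3 years. That is correct, but an expected limit just above 1 means roughly even odds, which is not the same as being able to rule equality out.

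Third, protocol 7.1 calls its scenarios hypothetical and says precision may change, SAP 8.1.4 describes the dilution under CR, and the interim analysis looks at observed event rates and allows extension. These soften the point, but none puts a number on the loss. Section 7.1 also sets no power target, so expected limits by analysis would serve as well as power. All eligible women enter by design and accrual has closed, so recruitment is not at issue.

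**Conclusion.** The point holds as a defect of stated precision. Table 3 has no input for stopping or switching and leaves the ratio undefined. Its limits can describe CR only if the ratio is ever-exposed. They are too narrow for AT whenever treatment ends before follow-up does. If the ratio is on-drug, CR estimates a smaller one.

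The size depends on on-drug time. Over 1 to 3 assumed years at the SAP's sample, AT power runs from 33% to about 75%, and diluted CR power from 12% to 61% (4.35 PY) or 14% to 70% (3.42 PY), against 88% or 80% with full persistence.

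A reader might infer a large fixed loss, since AT at 3 years is about 13 points below 88%. That does not generalise. Against the 3.42 PY implied by the stated loss rate, the AT shortfall at 3 years is about 5 points (79.8 − 74.5), and at 4 on-drug years AT power is 86%, close to 88%.

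The figures assume equal on-drug time in both groups, no excess VTE risk off drug and no switching between groups for CR, and no time gained for AT from women who switch into bazedoxifene. The SAP itself says CR bias runs towards the null in most cases but not all.

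**What to change.** In protocol 7.1:
- State whether the ratio in Table 3 is on-treatment or ever-exposed, and that the table counts all follow-up as exposed.
- Add AT rows for a stated range of mean on-drug time, for example 1, 1.5, 2 and 3 years, with matching CR rows showing the ratio expected under the declared off-drug assumption.
- Replace the claim that equality will be ruled out with a statement conditional on those assumptions, given as expected limits or as power.

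In SAP 3 and 5.4, judge AT precision on VTE events and person-years observed on drug. The prescription records already extracted should supply these, so the assumed range can give way to the actual figure.

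The cost is recalculation and text, with no further patients or data collection. The drawback for the sponsor is that stated precision becomes less favourable.
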